5.1 Discontinuation from IMP treatment

Subjects must be discontinued from IMP treatment and should continue in the trial for safety assessments only under the following circumstances:

- If the subject experiences 2 severe asthma exacerbations within a 12 consecutive months period
- If the subject is hospitalised due to asthma requiring treatment with systemic corticosteroids
- The subject experiences severe or persistent symptoms of oesophagitis
- If the subject becomes pregnant
- If, in the investigator's opinion, continuation with IMP treatment would be detrimental to the subject's well-being

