14.5 Database lock

When the database has been declared to be complete and accurate, the database will be locked, access for CRAs and non-sponsor staff/persons will be revoked and data may be unblinded.

If changes to trial data become necessary after database lock this must be performed according to the current ALK standard operating procedures (SOP).

A data archive for the site subject data files are produced and sent to the site. The investigator must sign and date the data archive approval form and send it back to the sponsor.

15 Statistical methods

Statistical analyses will be carried out by ALK Biometrics Department.

If nothing else is mentioned, all the statistical tests described in this section use a significance level of 5% and all tests and confidence intervals are two-sided. The null hypothesis is the hypothesis of no difference and the alternative to the null hypothesis is the hypothesis of a difference.

Descriptive statistics for numerical variables includes summary tables displaying mean, SD, median, 5%-quantile, 25%-quantile, 75%-quantile, 95%-quantile, minimum and maximum. Descriptive statistics for categorical variables includes frequencies tables that display numbers and percentage.

Before database lock, a separate statistical analysis plan (SAP) detailing the specifications given below will be prepared and agreed upon.

Any changes in the statistical methods compared to the final SAP will be documented in the ICTR. Post-hoc analyses, if any, will be clearly marked.

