15.1 Sample size and power considerations

The primary endpoint is the annualised rate of clinically relevant asthma exacerbations during the efficacy evaluation period (period 4). The rate of clinically relevant asthma exacerbations will be analysed using a negative binomial regression model.

From (Lanier et al. 2009) the rate of clinically relevant asthma exacerbations is expected to be approximately 1.4 exacerbations per subject per year. Over a period of 24 weeks the number of clinically relevant asthma exacerbation in the placebo group were 0.64 per subject (\sim 0.64*52/24 =1.4 per subject per year).

Power calculation are both performed based on the negative binomial distribution assuming overdispersion and based on the poisson distribution when assuming no overdispersion. Overdispersion means that some subjects will tend to have more exacerbations than others. The dispersion parameter in the negative binominal distribution is assumed to be k=0.7 (Pavord et al. 2012). When there is no overdispersion (k->0) the negative binominal distribution will become a poisson distribution.

Table 13 displays the sample size calculations for different values of the treatment effect expressed as the reduction in exacerbation rates for active treatment compared to placebo (100%*(PLB-ACT/PLB)). The power is set to 90% and sample size calculations are performed using a close formula for the negative binomial regression model (Keene et al. 2007):

$$N = \left\{ \frac{z_{1-\beta} + z_{1-\alpha/2}}{\log (\mu_1/\mu_2)} \right\}^2 \times \left\{ \frac{\mu_1 + \mu_2}{\mu_1\mu_2} + 2k \right\}$$

where N is the number of subject per treatment arm, μ_1 is the rate per subject in the given time interval for the placebo group, μ_2 is the rate per subject in the given time interval for the active group, $1 - \beta$ is the power, alpha is the level of significance and k is the dispersion parameter.

Table 13 Power	calculation
----------------	-------------

Power	Alpha	Time for efficacy assessment (weeks)	Rate PLB	Reduction (%) 100%*(PLB- ACT)/PLB)	μ ₁	μ2	k	N per arm (NB*)	N per arm (POIS)	
	0.05	34			0.91	0.63		334	219	
	0.05	52		30%	1.39	0.97		259	143	
	0.05	86			2.29	1.61		202	87	
0.9	0.05	34	1.4	25%	0.91	0.68	0.7	501	324	
	0.05	52			25%	1.39	1.04		389	212
	0.05	86			2.29	1.72		306	128	
	0.05	34			0.91	0.73		814	519	
	0.05	52			20%	1.39	1.11		635	339
	0.05	86			2.29	1.83		500	205	

PLB: placebo, ACT: active, NB: negative binominal, POIS: poisson distribution.

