### 4.3 Secondary endpoint analyses

For all secondary endpoints (key secondary and additional secondary endpoints), no data collected after treatment discontinuation is used.

Type of document Document ID	Date: Version: Status:	11-Aug-2022 4.0 Final	ALK
INTERNAL USE	Page:	32 of 79	

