#### 4.3.2.2 Asthma exacerbations

Time to first severe asthma exacerbation and time to first clinically relevant asthma exacerbation will be analysed by means of a Cox proportional hazards regression analysis. The model includes treatment and age group (<12 years/≥ 12 years) as effects. Region is included as a random effect assumed to follow a gamma distribution. Thus, this is a shared Cox gamma frailty model. The treatment comparison is performed using a Likelihood Ratio test based on the Cox proportional hazards regression model. The estimated hazard ratio (HR) of active treatment compared to placebo will be presented together with 95% Wald's confidence limits.

The Cox proportional hazards regression analysis is supplemented by a Kaplan-Meier analysis on time to first severe asthma exacerbation and time to first clinically relevant asthma exacerbation.

Time to recurrent clinically relevant asthma exacerbation and time to recurrent severe asthma exacerbation in days from the start of the efficacy period will each be analysed by means of an Andersen-Gill (AG) extension of the Cox model for recurrent events (Andersen and Gill 1982).

Type of document Document ID	Date: Version:	11-Aug-2022 4.0	
	Status:	Final	
INTERNAL USE	Page:	35 of 79	

The Andersen-Gill model assumes that events are independent, and so robust standard errors are used to accommodate heterogeneity. A Robust Sandwich covariance matrix will be used for the regression coefficient estimators. The treatment comparison is performed using a Likelihood Ratio test based on the extension of the Cox proportional hazards regression model. The model will include treatment and age group (<12 years/ ≥12 years) as fixed effects. The estimated hazard ratio (HR) of active treatment compared to placebo will be presented together with 95% confidence limits. In case of few recurrent clinically relevant asthma exacerbations or few recurrent severe asthma exacerbations, the endpoint(s) will only be summarised descriptively.

The annualised rate of severe asthma exacerbations in period 4 will be analysed similar to the primary efficacy endpoint using a NB regression model as described in section **4.2.3**.

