# 5 SAMPLE SIZE DETERMINATION

The primary endpoint is the annualised rate of clinically relevant asthma exacerbations during the efficacy evaluation period (period 4). The rate of clinically relevant asthma exacerbations will be analysed using a negative binomial regression model.

From (Lanier et al. 2009) the rate of clinically relevant asthma exacerbations is expected to be approximately 1.4 exacerbations per subject per year. Over a period of 24 weeks, the number of clinically relevant asthma exacerbation in the placebo group were 0.64 per subject ( $\sim$ 0.64\*52/24 = 1.4 per subject per year).

Power calculation are both performed based on the negative binomial distribution assuming overdispersion and based on the Poisson distribution when assuming no overdispersion. Overdispersion means that some subjects will tend to have more exacerbations than others. The dispersion parameter in the negative binominal distribution is assumed to be k=0.7 (**Pavord et al.**)

Type of document Document ID	Date: Version: Status:	11-Aug-2022 4.0 Final	
INTERNAL USE	Page:	43 of 79	

**2012)**. When there is no overdispersion  $(k \rightarrow 0)$  the negative binominal distribution will become a Poisson distribution.

**Table 5** displays the sample size calculations for different values of the treatment effect expressed as the reduction in exacerbation rates for active treatment compared to placebo (100%\*(PLB-ACT/PLB)). The power is set to 90% and sample size calculations are performed using a close formula for the negative binomial regression model (Keene et al. 2007):

$$N = \left\{ \frac{z_{1-\beta} + z_{1-\alpha/2}}{\log(\mu_1/\mu_2)} \right\}^2 \times \left\{ \frac{\mu_1 + \mu_2}{\mu_1\mu_2} + 2k \right\}$$

where N is the number of subjects per treatment arm,  $\mu_1$  is the rate per subject in the given time interval for the placebo group,  $\mu_2$  is the rate per subject in the given time interval for the active group,  $1 - \beta$  is the power, alpha is the level of significance and k is the dispersion parameter.

Power	Alpha	Time for efficacy assessment (weeks)	Rate PLB	Reduction (%) 100%*(PLB- ACT)/PLB)	μ 1	μ2	k	N per arm (NB*)	N per arm (POIS)
	0.05	34			0.91	0.63		334	219
	0.05	52		30%	1.39	0.97		259	143
	0.05	86			2.29	1.61		202	87
	0.05	34			0.91	0.68		501	324
0.9	0.05	52	1.4	25%	1.39	1.04	0.7	389	212
	0.05	86			2.29	1.72		306	128
	0.05	34			0.91	0.73		814	519
	0.05	52		20%	1.39	1.11		635	339
	0.05	86			2.29	1.83		500	205

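### The Andersen-Gill models for recurrent exacerbations censor children at IMP stops that their own exacerbations trigger; if children differ in underlying rate, the hazard ratio is pulled toward 1, and the sandwich variance does not correct that

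*SAP*

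**What the plan says.** SAP 4.3.2.2 fits an Andersen-Gill extension of the Cox model to recurrent clinically relevant exacerbations and, separately, to recurrent severe ones. Treatment and age group are the only effects. On within-child dependence it says: "The Andersen-Gill model assumes that events are independent, and so robust standard errors are used to accommodate heterogeneity". The gamma frailty in the same section is for region, and only in the time-to-first models. No subject frailty, event-history term or sensitivity analysis is given for the recurrent-event models.

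Three other places matter:

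- SAP 4.3: "For all secondary endpoints (key secondary and additional secondary endpoints), no data collected after treatment discontinuation is used".
- Protocol 5.1 lists events after which IMP must be stopped. One reads "If the subject experiences 2 severe asthma exacerbations within a 12 consecutive months period"; another is an asthma hospitalisation requiring systemic corticosteroids.
- On heterogeneity, SAP 5 explains: "Overdispersion means that some subjects will tend to have more exacerbations than others". Protocol 15.1 gives the value: "The dispersion parameter in the negative binominal distribution is assumed to be k=0.7".

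SAP 1.1.9 defines no estimand for the additional secondary endpoints, and SAP 2.1 leaves them out of the test hierarchy.

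**The concern.** Taken together, these rules mean that follow-up in the recurrent-event models can end because of the very events being modelled. The Andersen-Gill estimate needs the children still at risk to represent, within each arm, those who have left. If children differ in underlying rate, the stop rule removes the high-rate ones, and it removes more of them from the arm with more events. Rates within the risk sets then converge over time. A sandwich covariance describes the uncertainty of an estimate more honestly; it does not move the estimate.

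At stake is how two results from the same children are read. SAP 4.2.3 and 4.3.2.2 also analyse clinically relevant and severe exacerbations by negative binomial (NB) regression. If the Andersen-Gill hazard ratios sit closer to 1 than the NB rate ratios, a reader could take the gap as a weaker effect on repeat exacerbations, when part or all of it comes from the stop rule.

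**Working it through.** **Inputs from the documents.** Placebo rate: "the rate of clinically relevant asthma exacerbations is expected to be approximately 1.4 exacerbations per subject per year" (0.64 × 52/24 = 1.387). Dispersion k = 0.7, ratio of rates RR = 0.70 and 608 days of period 4 (Protocol 15.1 and 15.2.1). The stop rule is that of Protocol 5.1.

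**Assumed, because not in the documents.** The share of exacerbations that are severe: 30-70%, widened to 10-100%. The hospitalised share of severe events: 5%. RR = 0.70 also for severe events; the documents state it only for clinically relevant ones.

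**Step 1: reproduce the plan's figure.** N = {(z₀.₉₀ + z₀.₉₇₅)/ln(μ₁/μ₂)}² × {(μ₁+μ₂)/(μ₁μ₂) + 2k}. With μ₁ = 1.387 × 86/52 = 2.29 and μ₂ = 0.7μ₁ = 1.61, this is (3.24/0.357)² × (1.059 + 1.4) ≈ 203 per arm. Protocol Table 13 gives 202.

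**Step 2: who is removed.** With a gamma frailty Z (mean 1, variance k), a child with n events in t years at base rate λ has E(Z) = (1/k + n)/(1/k + λt). On placebo after one year, with 1/k = 1.43: no events gives 1.43/2.83 = 0.51; three events gives 4.43/2.83 = 1.57. The stop rule acts on children of the second kind.

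**Step 3: size at the sizing inputs.** Simulation of Poisson events given Z. Each event is severe with a fixed probability, the same in both arms. A child is censored at hospitalisation, at a second severe event within 365 days, or at 608 days, and the triggering event is counted. Age group is not modelled. The loss is 1 − ln(HR)/ln(0.70).

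| Setting | Stopped by rule, placebo / active | Andersen-Gill HR | Loss of log effect |
|---|---|---|---|
| No stop rule | none | 0.700 | 0 |
| Stop rule, k=0 | – | 0.700-0.701 | about 0 |
| Stop rule, k=0.7, severe share 30% | 17% / 11% | 0.722 | 8.6% |
| severe share 50% | 29% / 20% | 0.736 | 14.2% |
| severe share 70% | 40% / 29% | 0.750 | 19.5% |

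Severe shares of 10% and 100% give 2% and 25%. The severe-only Andersen-Gill model gives nearly the same values (0.721, 0.736 and 0.750 at shares 30%, 50% and 70%). An NB likelihood on the same censored data returns 0.700-0.704. The bias therefore needs both the stop rule and heterogeneity, and a subject-level gamma effect absorbs it.

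**Step 4: do the sizing inputs fit this trial?** SAP 5.1 reports that the first sample size reassessment gave 81% power at 900 subjects. From the formula in Protocol 15.2.1, power = Φ(|ln RR| × √[n(1−DR)/B] − 1.96), with B = (1+RR)²/(2 × μ_total × (τ/365) × RR) + 2k. Take μ_total = 1.4 × 1.7/2 = 1.19, τ = 608 and an assumed drop-out before period 4 of DR = 5% (Protocol Table 14 shows 9 of 325, 2.8%, in cohorts 1 and 2). Then B = 2.89/(2 × 1.19 × 1.666 × 0.7) + 1.4 = 2.44.

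- n = 300 per arm: Φ(0.357 × √(285/2.44) − 1.96) = 97%.
- n = 450 per arm: Φ(0.357 × √(427.5/2.44) − 1.96) = 99.7%, not 81%.

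A power of 81% needs B ≈ 6.75, so the blinded rate, the dispersion, or both differed from the sizing values. That is one equation for two unknowns. Pairs that satisfy it give:

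| Placebo rate per year | k | Loss at severe share 30% / 50% / 70% |
|---|---|---|
| 0.27 | 0.7 | 1.2% / 1.6% / 3.4% |
| 0.31 | 1.0 | 1.7% / 3.2% / 5.5% |
| 0.39 | 1.5 | 4.0% / 7.2% / 10.9% |
| 0.53 | 2.0 | 7.4% / 13.3% / 18.7% |
| 0.83 | 2.5 | 15.1% / 23.9% / 29.9% |

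**The case against.** Several points against this are fair.

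- **No target is missed, because none is set.** A reader might infer that these models fail the hypothetical, taken-as-instructed effect of SAP 1.1.9.3. The documents do not support that: SAP 1.1.9 defines no estimand here, and SAP Table 3 lists none. The yardstick can only be the on-treatment rate ratio. The artefactual gap to the NB results remains.
- **The 9-20% might be read as the bias in this trial.** It is not. The severe share is assumed, and the first reassessment contradicts the sizing inputs. The plan also sizes under a Poisson model, where the bias vanishes.
- **Few children stopped IMP and stayed.** SAP 1.1.9.3 counts only 3, while the sizing scenario implies rule-triggered stops in 17-40% of placebo children. The contrast is a reason for caution, but it does not count such stops: Protocol 9.4 allows trial discontinuation after a permanent IMP stop, and children who left at that time are censored in the same way.
- **The loss is small against precision.** With about 266 per arm (533 randomised, halved), the plan's variance gives a standard error of √(2.46/266) = 0.096. The bias of 0.031 to 0.070 (8.6% to 19.5% of 0.357) is about 0.3 to 0.7 of that. This stands, but a systematic shift does not shrink as the sample grows.
- **NB analyses cover the same events, and few recurrent events lead to description only.** Both are true. The fallback in SAP 4.3.2.2 has no threshold, so it cannot be relied on.

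**Conclusion.** The point holds as a conditional one. Given heterogeneity between children, event-triggered censoring biases both Andersen-Gill hazard ratios toward no effect, relative to the on-treatment rate ratio, and the sandwich matrix leaves that bias in place. The size is about 9-20% of the log effect at the sizing inputs with an assumed severe share of 30-70%. It is about 1-30% over the pairs examined that agree with the first reassessment, at the same severe shares and with 5% early drop-out assumed. With k=0 there is none. For severe events the figures further assume a ratio of 0.70.

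A reader might extend this to the primary result. The check does not support that: NB on the same censored data recovers the true ratio to within 0.004, so this mechanism leaves the primary analysis essentially untouched. No conclusion in the test hierarchy depends on the affected models. This is a cheap improvement, not a threat to the trial's main inference.

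**What to change.** In SAP 4.3.2.2, fit both recurrent-event models with a subject-level gamma frailty shared across a child's events. If the Andersen-Gill model with sandwich covariance is kept, label it descriptive and note that stops triggered by exacerbations pull it toward 1.

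Inverse-probability weighting for remaining on IMP is not a usable alternative. Once a trigger occurs the stop is mandatory, so the probability of remaining on IMP is zero under the protocol and positivity fails.

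The cost is a paragraph of SAP wording and one changed model. No new data are needed, and the stop rule stays as it is. The downside is reliance on the gamma assumption, which the primary NB model already makes. Whoever edits the paragraph should also state which treatment test goes with the frailty model. The likelihood ratio test now specified does not draw on the sandwich matrix, but that is a separate question from the bias described here.

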## **2** STATISTICAL HYPOTHESES

### 2.1 Multiplicity adjustment

The primary and key secondary endpoints will be controlled for multiplicity to ensure a maximum overall type I error rate of 5% in the hypothesis testing of these endpoints. The control for multiplicity is done by hierarchical testing, pre-specifying the order of the hypothesis to be tested. For all endpoints the null hypothesis to be tested is the hypothesis of no difference between treatment groups.

The order of hypothesis to be tested is:

- 1. Superiority testing of the HDM SLIT-tablet over placebo with respect to the rate of clinically relevant asthma exacerbations during the efficacy evaluation period (primary objective, section 1.1.1). The primary estimand will be used.
- 2. Superiority testing of the HDM SLIT-tablet over placebo with respect to proportions of days with nocturnal awakenings due to asthma which require SABA use during the 14 days eDiary period recorded every 4 months after randomisation (first key secondary objective, section **1.1.2**).
- 3. Superiority testing of the HDM SLIT-tablet over placebo with respect to the proportions of days with SABA use during the 14 days eDiary recording every 4 months after randomisation (second key secondary objective, section **1.1.2**).
- 4. Superiority testing of the HDM SLIT-tablet over placebo with respect to the percentage predicted FEV1 assessed every 4 months after randomisation (third key secondary objective, section **1.1.2**).

All hypotheses in the hierarchy are tested on a 5% significance level, i.e. significance is obtained when a p-value is below 5%. If the first hypothesis is statistically significant at the 5% level, i.e. the null hypothesis of no difference is rejected, then the second hypothesis is tested, and so forth. A hypothesis is only tested if all previously tested hypothesis were statistically significant at the 5% level, i.e. all previous null hypotheses were rejected.

Type of document Document ID	Date: Version: Status:	11-Aug-2022 4.0 Final		<
INTERNAL USE	Page:	27 of 79		

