# 5.1 Sample size reassessment

A blinded sample size reassessment (SSR) has been performed according to the protocol section 15.2.1. For each subject, the data cut-off-point for the SSR was the visit (including TCs) closest to but not before the 1st of February 2020.

Type of document	Date:	11-Aug-2022	
Document ID	Version:	4.0	
INTERNAL USE	Status: Page:	Final 44 of 79	

The conclusion of the SSR was that the reassessed sample size is 900 subjects, corresponding to a power of 81%. However, it was decided not to recruit for a new cohort as it was assessed that the SSR may not be accurate as the exacerbation rate was uncertain due to a very limited number of observations and due to the fact that the Covid-19 situation with rules of social distancing was likely to reduce transmission of respiratory infections, and thus also the number of exacerbations.

It was decided to perform a new SSR based on data sets from Cohort 1-3, however the SSR was not performed. Details are provided in section **4.8**.

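### SAP 4.3.2.2 prescribes a robust variance for the Andersen-Gill models but takes the treatment p-value from a likelihood ratio test that does not use it

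*SAP*

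**What the plan says.** Three consecutive statements in SAP 4.3.2.2 govern the two recurrent-event endpoints:

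- The reason for a robust variance: "The Andersen-Gill model assumes that events are independent, and so robust standard errors are used to accommodate heterogeneity".
- The remedy: "A Robust Sandwich covariance matrix will be used for the regression coefficient estimators".
- The test: "The treatment comparison is performed using a Likelihood Ratio test based on the extension of the Cox proportional hazards regression model".

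The model contains treatment and age group only. The hazard ratio is reported with 95% confidence limits. The SAP does not label these limits as robust, but that follows from the second statement. If recurrent events are few, the endpoints are summarised descriptively; no threshold is given.

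Nothing elsewhere changes this. Section 4.8 mentions only the time-to-first Cox models, section 7.2.3 covers only non-convergence, and section 7.2.5 gives code only for the primary negative binomial model.

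**The concern.** The likelihood ratio statistic is twice the difference of two log partial likelihoods, both computed as if a subject's events were independent. Asking for a sandwich covariance changes the standard error, the Wald test and the confidence limits, but leaves this statistic as it was. The correction that the SAP says is needed therefore never reaches the p-value.

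The plan expects the heterogeneity that causes the trouble. SAP section 5 assumes k=0.7 and explains: "Overdispersion means that some subjects will tend to have more exacerbations than others". Treatment and age group do not absorb it.

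A report could then show p<0.05 beside an interval that includes a hazard ratio of 1, with no rule for which governs. The same test is acceptable for the time-to-first models in that section, where each subject has at most one event and no sandwich is specified.

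**Working it through.** **1. The plan's own figure.** SAP Table 5, 86 weeks, 30% reduction, k=0.7, 90% power:

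- μ1 = 0.64 × 86/24 = 2.293; μ2 = 0.7 × 2.293 = 1.605.
- N = {(1.2816+1.9600)/ln(1/0.7)}² × {(μ1+μ2)/(μ1μ2) + 2k} = 82.59 × 2.459 = 203.1 per arm. The SAP gives 202, so the planning inputs are read correctly.

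**2. The rate implied by the reassessment.** SAP 5.1 reports that "the reassessed sample size is 900 subjects, corresponding to a power of 81" per cent. The formula in Protocol 15.2.1 can be solved for the pooled rate. Inputs: N=450 per arm, RR=0.7, 608 days, and drop-out before period 4 of 1 − 316/325 = 2.8% (cohorts 1 and 2 in Protocol Table 14; using it here is an assumption).

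- Multiplier: {(0.8779+1.9600)/0.3567}² = 63.30.
- 450 × (316/325)/63.30 = 6.912; less 2k = 1.4 leaves 5.512.
- Rate = 1.7²/(2 × 0.7 × (608/365) × 5.512) = 0.225 per year.

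The same result gives 0.18 per year at k=0 and 0.43 at k=2, so rate and k are not separately identified. Mean follow-up of 500-550 days would give 0.27-0.25 per year at k=0.7.

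**3. Analytic size of the error.** With gamma heterogeneity and mean count μ per subject, the null variance of the treatment coefficient is about (1+kμ) times the model-based variance. The likelihood ratio test's type I error is then about 2{1 − Φ(1.96/√(1+kμ))}.

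- 1.4 per year, 608 days: μ=2.33, 1+kμ=2.63, error 22.7%.
- 0.225 per year: μ=0.375, 1+kμ=1.26, error 8.1%.
- k=0: error 5.0%.

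**4. Simulation.** 20,000 null trials per scenario; 262 per arm (533 randomised less 9 at site 613, halved); gamma-Poisson events over 608 days; treatment the only covariate. The stopping rule matters because Protocol 5.1 ends treatment "If the subject experiences 2 severe asthma exacerbations within a 12 consecutive months period", and SAP 4.3 states that for secondary endpoints "no data collected after treatment discontinuation is used". Follow-up was therefore ended at the second severe event within 365 days. The documents give no severe share, so 25, 50 and 75% were assumed.

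| Endpoint, overall rate, k=0.7 | Likelihood ratio, type I error | Robust Wald |
|---|---|---|
| Clinically relevant, 1.4/yr, no stopping | 0.232 | 0.053 |
| Clinically relevant, 1.4/yr, stopping, 25/50/75% severe | 0.186 / 0.140 / 0.107 | 0.051 / 0.052 / 0.052 |
| Clinically relevant, 0.225/yr, no stopping | 0.078 | 0.050 |
| Clinically relevant, 0.225/yr, stopping, 25/50/75% | 0.082 / 0.074 / 0.075 | 0.053 / 0.049 / 0.053 |
| Severe, overall 1.4/yr, stopping, 25/50/75% | 0.072 / 0.076 / 0.079 | 0.052 / 0.052 / 0.051 |
| Severe, overall 0.225/yr, stopping, 25/50/75% | 0.055 / 0.061 / 0.067 | 0.045 / 0.049 / 0.052 |

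With k=0 and no stopping, the likelihood ratio test rejects in 5.1% (1.4/yr) and 5.0% (0.225/yr) of trials, which identifies heterogeneity as the cause.

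**5. Contradictory reports.** A second simulation of 2,000 trials per scenario included age group. At 1.4/yr, k=0.7, without stopping, it gave 0.235 against 0.053. The likelihood ratio p-value was below 0.05 with a robust interval containing 1 in 18.2% of null trials; the reverse never occurred. Because disagreement runs one way when k>0, its frequency in the table is the difference between the two columns. For clinically relevant events with stopping this is 2.2-2.9% at 0.225/yr and 5.5-13.5% at 1.4/yr.

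Not modelled: the hospitalisation rule, other drop-out (apart from a 20% drop-out variant of the second simulation: 0.230 against 0.058 at 1.4/yr) and the 7-day merging of events. Shorter follow-up would lower the inflation.

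**The case against.** The defect itself is hard to dispute; its size and importance are not.

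**The high figures belong to a superseded rate.** With a placebo rate of 1.4 per year (pooled 1.4 × 1.7/2 = 1.19), k=0.7 and RR=0.7, the reassessment formula gives 600 subjects about 97% power at 2.8% drop-out and 91% at 30%. Both exceed the 85% ceiling, so no increase would have been triggered. COVID-19 was also expected to lower rates. This stands: the 11-19% and 23% figures describe the design assumptions, not the trial as it was turning out. However, 0.225 per year is not an upper bound either. It depends on k=0.7, and the SAP itself calls the reassessed rate uncertain. Along the same curve, the analytic error without stopping is 10% at k=1 and 21% at k=2.

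**The severe analysis may never be run.** At 0.225 per year and k=0.7, about 3, 12 or 23 of 524 subjects would have two or more severe events for shares of 25, 50 and 75%, so the descriptive fallback could apply. That is fair for severe events, though the SAP does not define few. For clinically relevant events the count is about 37, and the test would probably be performed.

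**No controlled claim depends on it.** SAP 2.1 limits error control: "The primary and key secondary endpoints will be controlled for multiplicity". These endpoints have no estimand, and both event types are also analysed by negative binomial regression, which models overdispersion directly. This limits the consequence, but the p-value would still be reported at the 5% level and would still be wrong.

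**Conclusion.** The point holds: the specified p-value does not use the variance that the same paragraph says is required. When k>0 it is anti-conservative and can contradict the robust interval; when k=0 there is no problem.

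The most relevant size for clinically relevant events is about 7.4-8.2% instead of 5%, assuming k=0.7 and the rate implied by the reassessment. It would be larger if the true rate or k is higher. For severe events it is 5.5-6.7% at that overall rate. These figures rest on gamma heterogeneity, the assumed severe shares and the omissions listed above. The consequence is confined to two additional secondary endpoints; the primary analysis and the negative binomial analysis of the severe rate are unaffected.

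**What to change.** In SAP 4.3.2.2, replace the likelihood ratio sentence for the Andersen-Gill models. Take the treatment p-value from a robust Wald (or robust score) test using the sandwich covariance aggregated by subject, and state that the 95% confidence limits use the same covariance. Keep the likelihood ratio test for the time-to-first models.

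This costs one sentence and the matching analysis code, with no new data. The price is less favourable p-values for these two endpoints when events are overdispersed. If the change comes after the SAP is final, Protocol section 15 already requires it to be documented in the clinical trial report.
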